## 5.4 Secondary Endpoints

**MECHANISMS OF PAIRING TDCS WITH REHABILITATION.** *Hyp. 2:* Patients receiving tDCS with rehabilitation will exhibit larger gains in excitability of neural resources devoted to the weak triceps muscle (C7) and greater reductions in excitability of neural resources devoted to the spared biceps muscle (C5) compared with patients receiving rehabilitation alone. Patients receiving tDCS in rehabilitation will also exhibit larger gains in spinal excitability. Relationship between neural mechanisms and gains in strength and dexterity and functional abilities will be explored.

**SAFETY AND FEASIBILITY OF PAIRING TDCS WITH REHABILITATION.** *Hyp. 3:* Patients receiving tDCS with rehabilitation will show no greater adverse effects or attrition or ability to correctly guess the group allocation than those receiving rehabilitation alone.

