In accord with the proposed Aim 2, patients receiving tDCS during rehabilitation show greater gains in excitability of the brain and the residual descending pathways devoted to weak muscles. Although at baseline, patients show a greater number of excitable brain sites devoted to the stronger than the weaker muscles, in line with findings of injury-induced imbalances in excitability reported in earlier preclinical and clinical studies ( $t_7, 0.05 = 1.82, p = 0.05$ ) [20, 26-31], after tDCS, balance tends to become restored. The number of brain sites devoted to the stronger muscles tends to decrease ( $t_6, 0.05 = 1.07, p = 0.16$ ), whereas that devoted to the weaker muscles tends to increase after tDCS ( $t_6, 0.05 = 1.43, p = 0.1$ ) (fig. 4A, D). What is equally compelling is that such re-balancing is not witnessed after rehabilitation (without tDCS); instead, patients show further increase in the number of brain sites devoted to the strong muscles ( $t_4, 0.05 = 1.84, p = 0.07$ ). Therefore, the ratio of weak vs. strong muscle map in the motor cortices shows larger gains after tDCS than after rehabilitation, i.e., the ratio or the balance shifts in favor of the weak muscles ( $t_{10}, 0.05 = 1.92, p = 0.08$ ). Restoration of balance is associated positively with gains in strength of the weak muscles. Patients who show the greatest gain in the number of brain sites devoted to weak muscles also experience the greatest gains in strength of those muscles. Thus, tDCS helps re-balance or restore the excitability of surviving neural resources, plasticity that is functionally adaptive.

Regarding Aim 3 of the proposed study, patients receiving tDCS during rehabilitation experienced no serious adverse events. Further, these patients were not any more likely to guess which group they were in compared to patients who received sham tDCS ( $\chi^2 = 0.69; p = \text{N. S.}$ ). Thus, overall, the application of tDCS during rehabilitation is safe for individuals with SCI based on the findings of our pilot study. Our study also shows that it is feasible to test tDCS against a placebo condition in the proposed randomized, sham-controlled, double blind, phase I/II safety-efficacy clinical trial.

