Assessments will be completed before and after the baseline control phase (pretests 1/2), the intervention phase (posttest) and the 3-month follow-up phase (follow-up) (fig. 4). Assessments will include metrics of strength and dexterity (Graded Redefined Assessment of Strength, Sensation and Prehension [GRASSP]); functional abilities (Wolf Motor Function Test [WMFT]); activity limitations (self-care subscale of the Spinal Cord Independence Measure [SCIM]); and participation restrictions (Canadian Occupational Performance Measure [COPM]). TMS will be used to study excitability of neural resources devoted to a weaker muscle and a spared muscle. The Hoffmann reflex (H-reflex) involving peripheral electrical stimulation will be used to study spinal excitability. Up to 42 age-matched ( $\pm 5$  years), healthy control subjects will also undergo testing of TMS/H-reflex at a cross-sectional time-point. The goal will be to establish age-based norms for neurophysiologic metrics related to non-dominant biceps and triceps muscles. In accordance with feedback provided by DoD reviewers, adverse effects, SCI-specific symptoms (e.g., pain, autonomic dysreflexia) and attrition and integrity of blinding will also be recorded. The following aims and hypotheses will be tested in the proposed study.

Title: Improving Spinal Cord Injury Rehabilitation Interventions by Retraining the Brain

PI: [name]

Sub-site PI's: [name], [name], [name], [name], [name]

Protocol V 5.1 —2/3/2023

**Fig. 4: Study Design and follow-up procedures.** TMS= Transcranial Magnetic Stimulation; H-reflex= Hoffman Reflex; tDCS= transcranial direct current stimulation (tDCS)

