**Table 2: Sample Size Estimation based on Power Analysis**

	Outcomes/Metrics	Effect size (tDCS vs. Sham)	$\alpha$	80%	85%	90%	95%
Aim 1	UEMS (# Weak muscles showing clinically detectable improvement)	0.938	0.05	40	44	52	62
	$\Delta\%$ Nine Hole Peg Test	1.033	0.05	32	36	42	52
Aim 2	$\Delta\%$ Map Ratio (Weak map/Strong map)	1.192	0.05	26	30	34	40

estimate sample sizes, based on two sample t statistics compiled at  $\alpha = 0.05$  for 80% power (Table 2). For Aim 1, data concerning strength/power of muscles and dexterity (NHPT) was used since both of these metrics are components of the primary outcome for Aim 1 (GRASSP). Based on between-group comparison of the numbers of weak (C6-T1) muscles that achieved clinically detectable improvements on MRC ( $\geq 1$  full grade gain [63, 64]), we would require a total of 40 patients, and based on between-group comparison of % improvement on the NHPT (pegs per second), we would require 32 patients for achieving 80% power. This estimate would be sufficient for Aim 2 as well. For Aim 2, data concerning motor cortical map excitability was used, as this is the primary outcome for Aim 2. Based on between-group comparison of % change in map ratio (weak map/strong map), we would require 26 patients for achieving 80% power. Considering that there could be attrition of 10%, we expect to enroll 44 patients. A sample of 44 patients with 22 patients included in each SCI group would also be sufficient for study of Aim 3, which is designed to show that tDCS+-rehab is at least as safe and feasible (no greater attrition or probability of guessing the group) as rehabilitation given alone (sham+-rehab).

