## **9.4 Data Analysis Plan**

For aim 1, measures of function, strength/muscle power, dexterity, sensation, prehension, perception of independence in self-care, and quality of life will be collected, while for aim 2, metrics characterizing neurophysiology will be acquired and for aim 3, vital measurements will be noted daily.

Functional metrics adopted here are part of the National Institute of Neurological Disorders and Stroke (NINDS) Common Data Elements (CDEs), developed through the collaboration of the International Spinal Cord Society, the AIS, and the NINDS. The functional metrics span across all domains of the World Health Organization's (WHO's) International Classification of Function (ICF) model, including body function and structure, activity limitations, and participation restrictions. Metrics include Graded Redefined Assessment of Strength, Sensibility and Prehension (GRASSP), comprising the Upper Extremity Motor Score (UEMS) for strength, Nine-hole peg test (NHPT) for dexterity and sensation and prehension; Wolf Motor Function Test (WMFT) for measurement of functional abilities; Spinal Cord Independence Measure (SCIM) for evaluation of patient's ability to perform self-care; Canadian Occupational Performance Measure (COPM) to identify the patient's perceived level of daily participation in functional activities (e.g. cooking, cleaning, and hobbies). Each set of tests gives a different perspective of disability and testing all will allow us to get a full picture of patient function and quality of life before and after therapy. All measurements for aim 1 will take 120-150 min to complete. We will determine whether patients receiving tDCS in conjunction with rehabilitation experience greater recovery of function and independence than patients who receive rehabilitation alone (aim 1).

In aim 2, we will study the patient's neurophysiology, which will include the study of excitability of output pathways to a weaker muscle and a stronger muscle, and the cortical representations of these muscles. These measures of neurophysiology will be acquired using TMS and Hoffman or H-reflex. Neurophysiological tests will take 150-180 min to complete, which includes time allotted for breaks. We will test whether patients receiving tDCS in conjunction with rehabilitation experience greater gains in excitability of substrates devoted

Title: Improving Spinal Cord Injury Rehabilitation Interventions by Retraining the Brain

PI: [name]

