Sub-site PI's: [name], [name], [name], [name], [name]

Protocol V 5.1 —2/3/2023

to the weak muscle and larger decreases in the excitability of the substrates devoted to the stronger muscle than patients receiving rehabilitation alone (aim 2).

For aim 3, we will compare effects of interventions on patient's vital measurements, attrition, experience of adverse events (AEs) like tingling, itching, burning underneath the electrodes and likelihood of correctly guessing the group allocation. We anticipate that patients receiving tDCS in conjunction with rehabilitation will show no greater adverse effects or attrition than those receiving rehabilitation alone.

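### Comparing correct-guess rates between arms cannot show whether blinding held: it passes when both arms are equally unblinded and can fail when blinding is sound

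*Combined protocol and SAP*

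**What the plan says.** Blinding appears in four places in the plan, and only as a between-arm comparison of correct guessing wherever a comparison is described.

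- **5.4, Hyp. 3:** active patients will show "no greater adverse effects or attrition or ability to correctly guess the group allocation than those receiving rehabilitation alone".
- **5.2, text with Table 2:** Aim 3 is meant to show that active treatment is as safe and feasible as sham, explained as "no greater attrition or probability of guessing the group". The same paragraph states: "A sample of 44 patients with 22 patients included in each SCI group would also be sufficient for study of Aim 3".
- **9.4:** the quantities to be compared between interventions include the "likelihood of correctly guessing the group allocation". No test, margin or chance benchmark is given.
- **5.1:** "attrition and integrity of blinding will also be recorded", with no method of analysis.

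Section 4.1 reports the pilot in the same way: "these patients were not any more likely to guess which group they were in compared to patients who received sham tDCS", with a chi-square of 0.69, not significant. It then concludes that testing against placebo is feasible.

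**The concern.** Equal rates of correct guessing in the two arms are not evidence of blinding. If every patient in both arms knows the allocation, the rates are equal at 100% and Hyp. 3 is met. Conversely, patients may guess blindly but mostly hope or believe they had active stimulation. Active patients are then usually right and sham patients usually wrong, so the criterion fails although nobody knew anything. Because the wording is one-sided, it is also met when it is the sham patients who work out their allocation.

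This is one component of a secondary hypothesis, and no efficacy analysis in the documents uses the guess. It still matters. The trial is described as double-blinded, and Aim 1 includes the COPM, which records the patient's "perceived level of daily participation in functional activities". A reader will weigh such a measure by what the trial says about blinding. As worded, that statement could be favourable when most patients in both arms knew what they had received.

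**Working it through.** **Inputs.** The plan has 22 patients per arm (5.1, 5.2). That size was set for other aims: 5.2 gives 40 evaluable patients for an effect size of 0.938 at 80% power. A two-sided two-sample t-test gives 38, within 2 of the stated figure, and 40 x 1.10 = 44. No figure is stated for blinding, and no guess rates are given, so every rate below is an assumption.

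**Algebra.** Let a and s be the proportions guessing active in the active and sham arms.

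- Correct-guess rates are a (active) and 1-s (sham).
- The plan's contrast is a-(1-s) = a+s-1.
- The association of guess with arm is a-s.
- Bang's index (2 x proportion correct - 1) is 2a-1 for active and 1-2s for sham. The difference between the two indices is 2(a+s-1), and their sum is 2(a-s). The plan tests the difference, while tracking of allocation is in the sum.

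**One worked table.** Suppose 18/22 guess correctly in each arm, so a = 18/22 and s = 4/22.

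- Plan's contrast: 18/22 + 4/22 - 1 = 0; Fisher p = 1.0.
- Guess by arm: 18/22 - 4/22 = 14/22 = 64 points (Newcombe 95% CI 35 to 79); Fisher p = 0.00005.
- Bang's index in each arm: 2 x 0.818 - 1 = 0.64; Wald 95% CI 0.64 ± 1.96 x 2 x √(0.818 x 0.182/22), which is 0.31 to 0.96.
- At the extreme of 22/22 correct in both arms, p = 1.0 on the plan's contrast and 9.5e-13 for guess by arm.

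**Operating characteristics.** These are exact sums over two binomials with 22 per arm, using a two-sided Fisher test at 0.05 with every patient guessing active or sham. For the plan's contrast, only rejections with active more often correct count against Hyp. 3. For guess by arm, both directions count.

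| Assumed truth | Plan: active guesses better | Guess by arm flagged |
|---|---|---|
| Both arms 60% correct | 1% | 17% |
| Both arms 70% correct | 1% | 67% |
| Both arms 80% correct | 1% | 98% |
| Perfect blinding, 50% of both arms guess active | 1% | 2% |
| Perfect blinding, 60% guess active | 17% | 2% |
| Perfect blinding, 70% guess active | 67% | 2% |
| Perfect blinding, 80% guess active | 98% | 2% |
| Unequal: active 90% correct, sham 50% | 79% | 79% |
| Unequal: active 50% correct, sham 90% | about 5e-8 | 79% |

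With about 20 per arm after the 10% attrition allowed for in 5.2, the picture is the same. At 80% correct in both arms the figures are 1% and 96%. Under perfect blinding with 60%, 70% and 80% guessing active, the plan's contrast fails 14%, 60% and 96% of trials.

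**If no test is intended.** Read on observed rates alone, the criterion fails in about 40% to 44% of trials when both arms are equally correct at 50% to 90%. That rate does not rise with the degree of unblinding. Under perfect blinding with 60% guessing active, it fails in 88%.

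**The case against.** The arithmetic is not in dispute. The case for treating this as minor has five parts.

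- **The decision rule is partly imputed.** Hyp. 3 states an expectation, and 9.4 only says the arms will be compared. The percentages depend on the Fisher convention used here. That is fair, but the contrast is zero under equal unblinding whatever the test, and the reading without a test does no better.
- **No information is lost.** With a two-way guess, correct counts by arm convert exactly into a guess-by-arm table, so a report giving both rates would show 82% correct in each arm in the worked example. This stands, and it makes the repair cheap. It does not correct a stated hypothesis that would count that result as success.
- **The replacement is weak for modest unblinding.** At 60% correct in both arms, it flags only 17% of trials. This also stands, and is a reason to report intervals and not only a test.
- **The replacement has false alarms of its own.** If 75% of active and 35% of sham patients guess active purely because of perceived benefit, it is flagged in about 68% of trials. An effective treatment could produce that, so the result must be read as a signal.
- **The consequence is limited.** Section 5.2 names GRASSP as the primary outcome for Aim 1, and its strength and dexterity components are tested performance. This is why the point is a recommended change and not a threat to the primary analysis.

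The false-failure half also needs a clear lean toward active: at 55% guessing active, the failure rate is only about 5%.

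**Conclusion.** The concern holds. The only blinding comparison in the plan measures the lean of guesses toward active, not whether guesses follow allocation. With 22 per arm and an assumed 80% correct in both arms, it would point to a problem in about 1% of trials, against 98% for guess by arm. With perfect blinding it would fail 17%, 67% and 98% of trials if 60%, 70% and 80% of both arms guess active. It does detect unequal unblinding when active patients guess better (79% at 90% versus 50%), and practically never the reverse.

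The algebra needs no assumption about guess rates. The percentages rest on assumed rates, a two-way guess from every patient, and two-sided Fisher tests at 0.05. The documents do not show which scenario is likely. The pilot chi-square in 4.1, described as a between-arm comparison of guessing (8 active, 6 sham), does not exclude similar unblinding in both arms. The change should be made, but the primary efficacy analysis is not affected.

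**What to change.** In 5.2, 5.4 and 9.4, replace the correct-guess comparison with:

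1. a table of guess by allocated arm;
2. the between-arm difference in the proportion guessing active, with a 95% CI;
3. Bang's index for each arm, with a 95% CI.

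State that an association between guess and arm signals that blinding may have failed and does not prove it, because perceived benefit can produce the same pattern. State when the guess is taken, and interpret the result with that timing and, if recorded, the patient's reason for the guess. Do not infer intact blinding from equal correct-guess rates.

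The cost is small. The guess and the allocation are the data the planned comparison already needs, so this is mainly wording. The assessment schedule in 7.1b lists no guess form and the response format is not given, although the form may be described in material not supplied. A 'don't know' category should therefore be used only where the form already offers it, or for patients still to be assessed.

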## 6. SUBJECT SELECTION

### 6.1 Study Patient Population

Subjects participating in the study will be medically stable individuals who have been diagnosed with incomplete cervical spinal cord injury over 1 year ago and continue to have difficulties using one or both of their upper limbs. Subjects will be selected to participate in the study based on the inclusion/exclusion criteria listed below. Subjects will not participate in any study-specific tests or procedures before their written informed consent.

#### 6.1a General Inclusion Criteria

Patients with incomplete (having sparing to muscles in the upper extremities below the level of injury) C1-C8 SCI; age  $\geq 18$  years;  $\geq 1$  year time post injury (to avoid confounding effect of cervical root recovery [77]) will be enrolled. On the more affected side, patients will be required to have sparing of either the biceps or the triceps muscle, defined as  $\geq 3$ -muscle power grade on the MRC scale. They will also be required to show weakness of the muscle antagonist to the spared muscle i.e. triceps in case of spared biceps, or biceps in case of spared triceps on the affected side. Weakness will be defined as a MRC grade of 1-3, and a clinically detectable difference in power compared to the power of the spared muscle, i.e.,  $\geq 1$  muscle grade lower on the MRC scale [63, 64]. Criteria requiring sparing of one muscle and the weakness of the antagonist muscle are meant to create a homogeneous sample for the study of neurophysiology using TMS in Aim 2. These criteria will not be limiting for subject recruitment, as evident from the successful completion of our recent pilot work, because patients with cervical SCI either commonly show sparing of biceps (C5) and weakness of triceps muscles (C7), or this order of weakness is reversed in patients with central cord syndrome [60, 61]. On the contrary, these criteria will allow inclusion of even more-impaired individuals, who may not have “active hand function” as required by typical SCI studies [66, 68] and an ongoing study (NCT02611375).

#### 6.1b General Exclusion Criteria

Title: Improving Spinal Cord Injury Rehabilitation Interventions by Retraining the Brain

PI: [name]

Sub-site PI's: [name], [name], [name], [name], [name]

Protocol V 5.1 —2/3/2023

Patients with contraindications to tDCS and TMS, including pacemaker, metal in the skull, seizure history, or pregnancy will be excluded [75, 77]. Patients with spine stabilization will be included because the site of TMS/tDCS application to the head is distant from the site of the metal implant in the neck. Patients on an anti-spasticity or pain medication regimen will also be included, as long as the same dose and regimen are maintained. Patients with active pressure ulcers, however, will be excluded to avoid disruption of ongoing medical treatment. Patients with traumatic brain injury (TBI), diagnosed based upon acute injury Rancho scale <5 or positive MRI/CT findings at the time of injury will also be excluded to prevent confounding of TMS metrics. Patients with excessive tone/spasticity (Modified Ashworth Scale [MAS] >3) and severe contractures or soft tissue shortening at elbow/wrist will be excluded. Finally, patients participating in ongoing upper-limb therapies will be excluded to minimize the possibility of confounding effects. For healthy control participants, the exclusionary criteria will be the same as mentioned above. Healthy control inclusion criteria is age between 18-70 years old, without any diagnosis of neurological disease.

## 6.2 Subject Recruitment

Patients will be recruited via methods found successful in the PI's recent pilot trial (NCT01539109), funded by the Department of Defense. Patients will be recruited from 9 area hospitals within the Cleveland Clinic, from outpatient and community-based programs, support groups, and referrals. We will also enroll directly from Cleveland Clinic Physician [name]. [name] is new to the Cleveland Clinic, however he has held the largest practice for SCI in NE Ohio for decades. Therefore, his patients who visit him at CCF will serve as the ideal candidate population. [name] and the Research Personnel will tell his patients about research studies when they arrive for their exam visit. Enrolling past trial participants will also prevent delays in enrollment. Those on the Pilot study's waiting list could be contacted for the proposed study. Subject recruitment will be significantly enhanced through the use of Cleveland Clinic's KP, which logs each neurological outpatient visit within Cleveland Clinic and therefore provides valuable long-term and follow-up information, aiding in study recruitment. KP will be used to request a list of potential participants. KP generates a list of patients seen at a particular center at the Cleveland Clinic that can be filtered by certain center metrics. We will send KP request to centers at the Cleveland Clinic that have been known or are suggested to us by site physicians at location on campus that SCI patients are seen. KP then will send us the password protected list and we will save on our private server with a password protection only known to lab personnel. Patients of the KP query that seem to be a potential fit will have a letter sent to their physician to see if we can contact their subject in regards to our study and potentially screen. Another recruitment method we will adopt is the use of eResearch and an EPIC heat request. eResearch Requests allows us to request patient MRN's from the Cleveland Clinic medical records system that fit a certain criteria that we provide. From this request we will be receiving monthly exports from the eResearch team with the names of individuals which fit the request filters we initially provided to them. Epic Heat requests will allow us the ability to request a report of patient MRNs from the EPIC team based on a set criteria for participants to fit are inclusion criteria. We will save these Excel sheets sent to us by the respective teams as password protected documents and review the MRNs through our usual

Title: Improving Spinal Cord Injury Rehabilitation Interventions by Retraining the Brain

PI: [name]

Sub-site PI's: [name], [name], [name], [name], [name]

Protocol V 5.1 —2/3/2023

chart review method. After subjects are identified we will follow our usual route of contacting subjects which involves sending physician letters via email or EPIC Messaging, then send the patient letters via physical postal mail or EPIC Messaging/MYCHART to those patients that physicians do not say no to sending a letter, and then calling the potential participants after 1-2 weeks to gauge their interest in participating if they do not call us first.

In addition, we will be working with our partners at Select Medical to identify potential candidates housed in their acute rehab hospitals (Edwin Shaw, Avon, and Beachwood) and provide study fliers/brochures to them via intake binders or advertisements placed at the facilities. It is anticipated that these patients in Select Medical CCF acute rehabilitation hospitals will not meet the 1 year post-cervical spinal cord injury inclusion criteria for the study, however, providing these potential participants with our study information may help give the patients an idea of what avenues they can pursue upon completion of their clinical care. As a preparatory step in research, if an interested candidate reaches out to us, we will perform phone screening even though they will not meet our time post injury criteria. This will allow us to identify any immediate exclusionary criteria related to the study protocol and provide input to the interested candidate on their potential for participation after their clinical care.

[name] has also created links with the many agencies and support group for SCI survivors across Ohio, on which she has relied or help with patient recruitment.

We also will potentially use the following for posting advertisements in the region and nationwide: National Spinal Cord Injury Association Newsletter, Publications of the Paralyzed Veterans of America, Local Newspapers, Posting the clinical trial on SCOPE ([www.scope-sci.org](http://www.scope-sci.org)), nationally on clinicaltrials.gov.

A Brochure and flyer will also be used to advertise for the study.

